10.5.2.2 Adverse events (AEs)

Summary tables for adverse events (AEs) will include only AEs that started or worsened during the on-treatment period, the **treatment-emergent** AEs. However, all safety data (including those from the pre and post-treatment periods) will be listed and those collected during the pre-treatment and post-treatment period will be flagged.

The incidence of treatment-emergent adverse events (new or worsening from baseline) will be summarized by system organ class, preferred term, severity (based on CTCAE grades), type of adverse event, relation to study treatment, and dose level. Deaths reportable as SAEs and non-fatal serious adverse events will be listed by patient and tabulated by type of adverse event and dose level.

Specific safety event categories (SEC) will be considered. Such categories consist of one or more well-defined safety events which are similar in nature and for which there is a specific

clinical interest in connection with the study treatment(s). For each specified SEC, number and percentage of patients with at least one event part of the SEC will be reported.

DLTs will be listed and their incidence summarized by primary system organ class, worst grade, type, and dose level. The dose determining set will be used for these summaries.

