In addition to identifying common target organ toxicities understanding the metabolism and elimination of each compound and how the presence of one compound might impact systemic drug concentrations of the other can further inform the potential for additive or synergistic toxicities. Based on in vitro metabolic profiling and results from clinical PANOBINOSTAT drug interaction studies, PANOBINOSTAT has shown to be a non-sensitive CYP3A substrate and a weak CYP2D6 inhibitor in patients. It has also been predicted to have minimal clinical risk with a non sensitive CYP3A substrate. RUXOLITINIB is also a non-sensitive CYP3A substrate and is not known to be a CYP inhibitor or inducer. Since CYP3A is the most abundant CYP enzyme, drugs with shared elimination pathway via CYP3A have not been shown to have compromised elimination. Therefore drug-interaction between PANOBINOSTAT and RUXOLITINIB is not expected by being CYP3A substrates. PANOBINOSTAT is a weak time-dependent CYP3A inhibitor and predicted to have no consequence on a non-sensitive CYP3A substrate, such as RUXOLITINIB. Since PANOBINOSTAT is also administered intermittently, its clinical impact on the chronic RUXOLITINIB administration is deemed even more remote. Based on available in vitro and clinical data, clinical drug interaction between PANOBINOSTAT and RUXOLITINIB is not expected. Based on preclinical data a summary of the integrative assessment for potential for additive and/or synergistic toxicity of combining PANOBINOSTAT with RUXOLITINIB is presented below.

Table 1-4 Integrative toxicological assessment of PANOBINOSTAT (LBH589) / RUXOLITINIB (INC424) combination

Target Organ	LBH589	INC424	Potential Impact of Combination
Genotoxicity	Positive in Ames and Chromosomal Aberration Assays	Not genotoxic	None predicted
Cardiovascular	QT prolongation (dog, human)	↓ in blood pressure, ↑ heart rate (dog), ↓ respiratory minute volume (rat) minimal heart fibrosis (rat)	None predicted ^a

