	
 i. Progressive splenomegaly that is defined by the appearance of a previously absent splenomegaly that is palpable at greater than 5 cm below the left costal margin or a minimum 100% increase in palpable distance for baseline splenomegaly of 5-10 cm or a minimum 50% increase in palpable distance for baseline splenomegaly of greater than 10 cm. ii. Leukemic transformation confirmed by a bone marrow blast count of at least 20%. iii. An increase in peripheral blood blast percentage of at least 20% that lasts for at least 8 weeks.
5. Stable disease (SD)	None of the above.
6. Relapse	Loss of CR, PR, or CI. In other words, a patient with CR or PR is considered to have undergone relapse when he or she no longer fulfills the criteria for even CI. However, changes from either CR to PR or CR/PR to CI should be documented and reported.

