7.2 Assessment types

7.2.1 Disease progression

Disease progression will be documented by a $> 25\%$ increase in spleen length by palpation compared to the on-study nadir **or** by disease symptoms progression based on the Investigator's expert judgment **or** by a significant increase in blood or bone marrow blasts consistently for at least 2 weeks that in the expert opinion of the Investigators indicates progression of disease. Bone marrow biopsies are not required to document progression, however may be performed as clinically indicated and at the discretion of the investigator. If performed, findings should be documented in the eCRF.

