8.1 Adverse events

8.1.1 Definitions and reporting

An adverse event is defined as the appearance of (or worsening of any pre-existing) undesirable sign(s), symptom(s), or medical condition(s) that occurs after patient's signed informed consent has been obtained. Abnormal laboratory values or test results occurring after informed consent constitute adverse events only if they induce clinical signs or symptoms, are considered clinically significant, require therapy (e.g., hematologic abnormality that requires transfusion or hematological stem cell support), or require changes in study medication(s).

Adverse events that begin or worsen after informed consent should be recorded in the Adverse Events eCRF. Conditions that were already present at the time of informed consent should be recorded in the Medical History eCRF. Adverse event monitoring should be continued for at least 30 days following the last dose of study treatment. Adverse events (including lab abnormalities that constitute AEs) should be described using a diagnosis whenever possible, rather than individual underlying signs and symptoms. When a clear diagnosis cannot be identified, each sign or symptom should be reported as a separate Adverse Event.

Adverse events will be assessed according to the Common Terminology Criteria for Adverse Events (CTCAE) version 4.03. If CTCAE grading does not exist for an adverse event, the severity of mild, moderate, severe, and life-threatening, corresponding to Grades 1 - 4, will be used. CTCAE Grade 5 (death) will not be used in this study; rather, information about deaths will be collected through a Death form.

The occurrence of adverse events should be sought by non-directive questioning of the patient (subject) during the screening process after signing informed consent and at each visit during the study. Adverse events also may be detected when they are volunteered by the patient (subject) during the screening process or between visits, or through physical examination, laboratory test, or other assessments. As far as possible, each adverse event should be evaluated to determine:

1. The severity grade (CTCAE Grade 1-4)
2. Its duration (Start and end dates)
3. Its relationship to the study treatment (Reasonable possibility that AE is related: No, Yes) or

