Its relationship to the study treatment (Reasonable possibility that AE is related: No, Yes, investigational treatment, Yes, the study treatment (non-investigational), Yes, both and/or indistinguishable)
4. Action taken with respect to study or investigational treatment (none, dose adjusted, temporarily interrupted, permanently discontinued, unknown, not applicable)
5. Whether medication or therapy taken (no concomitant medication/non-drug therapy, concomitant medication/non-drug therapy)
6. Whether it is serious, where a serious adverse event (SAE) is defined as in Section 8.2.1.

All adverse events should be treated appropriately. If a concomitant medication or non-drug therapy is given, this action should be recorded on the Adverse Event eCRF.

Once an adverse event is detected, it should be followed until its resolution, it is judged as no longer clinically significant by the investigator, stable or until it is judged to be permanent. Assessment should be made at each visit (or more frequently, if necessary) of any changes in severity, the suspected relationship to the study treatment, the interventions required to treat it, and the outcome.

Progression of disease (including fatal outcomes), if documented by use of appropriate method should not be reported as a serious adverse event.

Adverse events separate from the progression of disease (example, deep vein thrombosis at the time of progression or hemoptysis concurrent with finding of disease progression) will be reported as per usual guidelines used for such events with proper attribution regarding relatedness to the drug.

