8.2 Serious adverse events

8.2.1 Definitions

Serious adverse event (SAE) is defined as one of the following:

- Is fatal or life-threatening
- Results in persistent or significant disability/incapacity
- Constitutes a congenital anomaly/birth defect
- Is medically significant, i.e., defined as an event that jeopardizes the patient or may require medical or surgical intervention to prevent one of the outcomes listed above
- Requires inpatient hospitalization or prolongation of existing hospitalization, unless hospitalization is for:
 - Routine treatment or monitoring of the studied indication, not associated with any deterioration in condition (specify what this includes)
 - Elective or pre-planned treatment for a pre-existing condition that is unrelated to the indication under study and has not worsened since signing the informed consent
 - Treatment on an emergency outpatient basis for an event not fulfilling any of the definitions of a SAE given above and not resulting in hospital admission
 - Social reasons and respite care in the absence of any deterioration in the patient's general condition
- Protocol exempt SAEs: Progression of disease (including fatal outcomes), if documented by use of appropriate method (for example, as per IWG criteria for treatment response in myelofibrosis with myeloid metaplasia (Tefferi 2006)), should not be reported as a serious adverse event. However, other adverse events associated with disease progression (PD) but not a typical component of PD such as thrombosis, must be reported as appropriate, per AE/SAE criteria.

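### The only by-dose death table is limited to SAE-reportable deaths, so deaths from documented progression fall outside it and leukemic transformation can fall outside the SAE table

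*Combined protocol and SAP*

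**What the plan says.** Section 10.5.2.2 sets the rule for deaths: "Deaths reportable as SAEs and non-fatal serious adverse events will be listed by patient and tabulated by type of adverse event and dose level".

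Which deaths count as SAEs is settled earlier. Section 8.2.1 has a class of "Protocol exempt SAEs: Progression of disease (including fatal outcomes), if documented by use of appropriate method", with the IWG response criteria named as an example of such a method. Section 8.1.1 repeats the rule: "Progression of disease (including fatal outcomes), if documented by use of appropriate method should not be reported as a serious adverse event".

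Table 4-1 (Section 4.1) lists among the IWG criteria for progressive disease "Leukemic transformation confirmed by a bone marrow blast count of at least 20" percent. Section 7.2.1 gives a separate definition of progression, one limb of which is "a significant increase in blood or bone marrow blasts consistently for at least 2 weeks", judged by the investigators.

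Section 8.1.1 also drops CTCAE Grade 5 and says instead that "information about deaths will be collected through a Death form". Leukemic transformation is not among the events of special interest in Section 8.1.3.

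**The concern.** Safety and tolerability are the Phase I primary objective (Section 10.4), and the RPTD decision draws on tolerability beyond Cycle 1 (Sections 6.2.3 and 6.2.3.2). The trial is single-arm, open-label and single-center, with no data monitoring committee (Section 8.6) and no site monitoring (Section 9.1). Whether a death is classed as progression is therefore an unblinded local judgment that no control arm can check, and under 10.5.2.2 that judgment decides whether the death is counted in the table.

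The distinction is hard to draw in this disease. Section 1.1 names infection and bleeding from marrow failure, and transformation to AML, among the commonest causes of death in myelofibrosis. Thrombocytopenia, hemorrhage and infection are also events of special interest for the combination (Section 8.1.3).

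Leukemia is a reasonable event to watch. Table 1-4 records panobinostat as "Positive in Ames and Chromosomal Aberration Assays", Section 8.4 speaks of potential genotoxicity, and Section 2.3 reports AML as a reason for stopping treatment in 1.3% of patients in an earlier single-agent ruxolitinib study.

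**Working it through.** **Tracing the rules**

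1. A death is tabulated under 10.5.2.2 if it is reportable as an SAE.
2. A fatal event is an SAE under 8.2.1 unless it is documented progression, which 8.1.1 and 8.2.1 exempt.
3. The IWG criteria are one accepted form of documentation (8.2.1). Under Table 4-1 they include leukemic transformation. The exemption does not name leukemia; the link comes from reading 8.2.1 with Table 4-1.
4. With Grade 5 not used, the AE tables by severity do not show deaths either.
5. No other table of deaths and no leukemia category is specified. Deaths from other causes remain SAEs and are tabulated.

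**The boundary of the exempt set**

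| | Table 4-1 (IWG) | Section 7.2.1 |
|---|---|---|
| Spleen | New splenomegaly palpable at more than 5 cm, or a 100% or 50% increase depending on baseline size | More than 25% increase over on-study nadir |
| Blasts | Marrow blasts of at least 20%, or a peripheral blast increase of at least 20% lasting at least 8 weeks | Significant increase for at least 2 weeks, by investigator opinion; marrow not required |
| Symptoms | Not a criterion | Progression by investigator judgment |

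The two definitions can exempt different deaths, and 8.2.1 offers IWG only as an example.

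**The plan's own safety figure**

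Sections 10.4.2.2 and 10.8 justify 22 patients by a 90% chance of seeing an AE of 10% incidence. This is reproduced: 1 − 0.9^22 = 0.9015.

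For scale, apply the same formula, 1 − (1 − p)^n, to assumed rates p of leukemia or progression death:

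| p | n = 22 | n = 58 |
|---|---|---|
| 1.3% (Section 2.3, discontinuations only) | 25% | 53% |
| 5% (assumed) | 68% | 95% |
| 10% (assumed) | 90% | 99.8% |

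These are chances that at least one event occurs. An exempted event stays out of the SAE and death table at any rate, so a zero there says nothing about it. If all such events were counted and none occurred in 22 patients, the exact one-sided 95% upper limit would be 1 − 0.05^(1/22) = 12.7%.

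**How many deaths of any cause might occur**

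Assume exponential survival over 7 months, standing for induction plus six cycles. Seven 28-day periods are 196 days, about 6.4 calendar months, so this slightly overstates.

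| Survival figure assumed | Formula | Mortality | Of 22 |
|---|---|---|---|
| DIPSS-Plus medians, 35 and 16 months (Section 1.1) | 1 − exp(−ln2 × 7/35); 1 − exp(−ln2 × 7/16) | 12.9%; 26.2% | 2.8; 5.8 |
| DIPSS medians, 4 and 1.5 years (Section 1.1), the score used for eligibility | 1 − exp(−ln2 × 7/48); 1 − exp(−ln2 × 7/18) | 9.6%; 23.6% | 2.1; 5.2 |
| COMFORT-1 ruxolitinib survival, 0.98 and 0.84 (Section 1.3.3), read as one-year values (assumption) | 1 − 0.98^(7/12); 1 − 0.84^(7/12) | 1.2%; 9.7% | 0.3; 2.1 |

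The range is about 0.3 to 6 deaths of 22.

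**The case against.** The strongest reply is that little is lost. Section 10.5.2.2 itself says all safety data will be listed, including pre- and post-treatment data. Section 10.5.1 has all recorded AEs listed and summarized, and other safety information tabulated where appropriate. The Death form carries no SAE restriction, and Section 7.1.5.1 includes death and progression among withdrawal reasons. With 33 to 58 patients, a reader could count deaths from listings. The exemption concerns SAE reporting and does not expressly bar recording leukemic transformation as an AE. Such a case would also count as progressive disease in the response assessment. DLT counting over Days 1–28 is unaffected.

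Most of this stands. A reader might infer that the safety tables omit deaths and leukemias in general, and the documents do not support that. Only deaths from documented progression leave the specified table, and leukemia may still be in the AE tables. Nor do the documents describe an established genotoxic hazard of the combination: Table 1-4 predicts no combined genotoxic impact, and the 1.3% AML figure concerns ruxolitinib alone.

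What the reply does not remove is the restrictive rule. A listing is not a by-dose count, and tabulation where appropriate leaves the choice until the data are seen. Section 8.1.1 also contrasts AEs that are separate from progression with progression itself, so whether leukemia will be recorded as an AE is uncertain.

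**Conclusion.** The point holds in limited form. Under the stated rules, deaths attributed to documented progression are outside the only by-dose death table, and leukemic transformation can be outside the SAE table. The boundary of what is exempt is not fixed, because Section 7.2.1 and Table 4-1 differ and must be reconciled.

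Its size in deaths is uncertain. The 0.3 to 6 of 22 is deaths of any cause and rests on exponential survival and on which survival figures are chosen. It should not be turned into a number of missing deaths: that needs the fraction attributed to progression, which the documents do not give. Patients who progress must also leave the study (Section 7.1.5.1), so some of these deaths may fall more than 30 days after the last dose. No effect on the MTD or the Phase II response endpoint is shown. This is a cheap improvement to safety reporting.

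**What to change.** In Section 10.5.2.2, replace the restriction to SAE-reportable deaths with all deaths recorded on the Death form. List and tabulate them by dose level, cause and period (on-treatment and post-treatment, as defined in Section 10.5.2.1), whatever their SAE status. Since Section 7.1.6 plans only 30 days of follow-up after the last dose, a footnote should say that later deaths are those that came to be recorded.

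Make leukemic transformation its own safety event category, a mechanism 10.5.2.2 already provides, counted whether or not it is an SAE. Reconcile Section 7.2.1 with Table 4-1 and state which definition governs the exemption in 8.1.1 and 8.2.1.

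The cost is one or two table shells, using the Death form and blast counts already collected. SAE reporting rules, visits and sample size need not change. The reported death count may look less favorable.

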10.5.2.3 Laboratory abnormalities

For laboratory tests covered by the Common Terminology Criteria for Adverse Events (CTCAE) version 4.03 (NCI 2009), the study's biostatistical and reporting team will grade laboratory data accordingly. For laboratory tests covered by CTCAE, a grade 0 will be assigned for all non-missing values not graded as 1 or higher. Grade 5 will not be used. For laboratory tests where grades are not defined by CTCAE, results will be graded by the low/normal/high classifications based on laboratory normal ranges. The following by-treatment summaries will be generated separately for hematology and biochemistry laboratory tests:

- frequency table for newly occurring on-treatment grades 3 or 4 (see below for details)
- shift tables using CTCAE grades to compare baseline to the worst on-treatment value
- for laboratory tests where CTCAE grades are not defined, shift tables using the low/normal/high/(low and high) classification to compare baseline to the worst on-treatment value.
- listing of all laboratory data with values flagged to show the corresponding CTCAE grades and the classifications relative to the laboratory normal ranges. Time to onset of grade 3 or higher SECs will be summarized by dose level.

10.5.2.4 Other safety data

Data from other tests (e.g., electrocardiogram or vital signs) will be listed, notable values will be flagged, and any other information collected will be listed as appropriate by study phase. Any statistical tests performed to explore the data will be used only to highlight any interesting comparisons that may warrant further consideration.

10.5.2.5 Supportive analyses for secondary objectives

No supportive analyses for secondary objectives are planned.

10.5.2.6 Tolerability

Not applicable

10.5.3 Biomarkers

See [Section 7.2.10](#).

10.5.4 Resource utilization

Not applicable

10.5.5 Patient-reported outcomes

Not applicable

10.6 Exploratory objectives

The following exploratory efficacy objectives will be included on the study:

10.6.1 To assess preliminary efficacy of the combination of RUXOLITINIB and PANOBINOSTAT by physician palpation in all dosing cohorts

Spleen measurements by palpation will be obtained with a primary emphasis on the change in measurements from baseline to Week 12. Descriptive statistics will be provided for the spleen length and percent change from baseline over time. The proportions of patients with at least a 50% reduction in palpable spleen length at any time point, at week 12 and at week 24 will be summarized. This analysis will be done separately on patients in every dosing cohort, as well as, on the pooled patients, in the escalation phase.

10.6.2 To assess the preliminary efficacy at the MTD and/or RPTD by the use of MRI/CT

The endpoint for this objective will be the volumetric reduction in spleen size from baseline to Week 12 (or end of study, whichever comes early), as assessed by MRI/CT. The analysis will be restricted to patients in the expansion phase, who are dosed at the MTD and/or RPTD. Responders (defined as those achieving at least 35% reduction in splenic volume (compared to baseline), at week 12 or end of study, whichever comes first), will be summarized in terms of percentage rates of response, along with 95% confidence intervals. An **exact binomial confidence interval** (implemented using SAS procedure FREQ with EXACT statement for one-way tables) will be calculated (Clopper 1934). Descriptive statistics for the volumetric reduction in spleen size and percent change (from baseline) at the end of week 24 will also be provided. Since preclinical studies suggest a synergistic effect of the two agents in combination, we would expect a spleen response rate (>35% reduction in spleen volume by MRI) of >30% as was assumed in the COMFORT study. Since the proportion of patients obtaining this efficacy endpoint was 42% in COMFORT-1, we will have a target response for this secondary endpoint of >50%, and this will be reported in a descriptive manner.

10.6.3 To assess (preliminary) efficacy of the combination of RUXOLITINIB and PANOBINOSTAT by bone marrow biopsy in all dosing cohorts

The endpoint for this objective will be the change in bone marrow histomorphology from aspirate and/or biopsy samples collected at baseline as compared to Cycle 6 (+/- 1 week), and any subsequent biopsies. The change in fibrosis will be assessed, and graded according to the International Working Group (IWG) consensus criteria for treatment response (Tefferi 2006).

10.6.4 To explore biomarkers at the MTD and/or RPTD (including but not limited to: JAK2V617F allele burden, genetic mutations impacting the molecular pathogenesis of MF other than JAK2V617F , and cytokine measures)

Exploratory biomarker analysis include (but are not limited to) the following, JAK2V617F allele burden, genetic mutations impacting the molecular pathogenesis of MF other than JAK2V617F, and cytokine measurement (all done pre and post treatment).

Unless otherwise specified, all statistical analyses of biomarker data will be performed on the FAS with the related measures. Data transformations, such as base 2 logarithms, may be used prior to summarizing and analyzing the data.

Although analyses are described herein, data synergies may be realized through correlation of biomarker data with other biomarker and/or clinical response variables. In addition, other post-hoc exploratory assessments are expected and may be performed.

Summary statistics in absolute values at each visit and absolute and percentage change from baseline at each visit will be provided for JAK2V617F allele burden, and cytokine measurement.

Exploratory correlation of the biomarker levels at baseline or their post-treatment changes with clinical response variables will be performed depending on trial outcome.

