On November 16, 2011, Ruxolitinib was approved by the U.S. Food and Drug Administration (FDA) for the treatment of intermediate/high-risk MF based upon the combined results of the COMFORT-I and COMFORT-II Trials. The *CO*ntrolled *M*yelo*F*ibrosis Study with *O*ral JAK2 inhibitor *T*reatment (COMFORT-1) study was a randomized (1:1), double-blinded phase III study sponsored by Incyte comparing Ruxolitinib to placebo in patients with intermediate-2 or high risk MF and a baseline platelet count of at least $100 \times 10^9/L$ (25). Oral ruxolitinib was dosed at 15mg BID for patients with platelet counts between $100-200 \times 10^9/L$ and 20mg BID for patients with $>200 \times 10^9/L$. A total of 309 patients were randomized (ruxolitinib 155, placebo 154), with a median age of 68 years. The primary endpoint of this study was a reduction in spleen volume of at least 35% by either MRI/CT. The 35% reduction in spleen volume was chosen based on previous studies that established a correlation of 35% reduction in volume by imaging to approximately 50% reduction by manual palpation on physical exam. Secondary endpoints included assessment of duration of spleen reduction and improvement in disease related symptoms as assessed by the MFSAF (myelofibrosis symptom assessment form) (26). Patients were allowed to crossover from placebo if they had a greater than 25% increase in spleen volume by imaging from baseline and all patients were un-blinded and could crossover when every patient had completed week 24 or discontinued the treatment and 50% of remaining patients had completed week 36.

Grade 3/4 anemia was the most frequent hematologic AE observed in 45% vs 19.2%, in the ruxolitinib vs placebo arm, respectively. Grade 3/4 thrombocytopenia was observed in 12.9% vs 1.3% in patients treated with ruxolitinib vs placebo, respectively. Neutropenia that was grade 3/4 was observed in 7.1% vs 2% in the ruxolitinib vs placebo arm, respectively. The most common non-hematologic adverse event seen of any grade in the ruxolitinib treated group was diarrhea 23.2% (compared to 21.2% in placebo group). All in all, this was a well-tolerated drug.

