At 24 weeks, 41.9% of patients treated with ruxolitinib experienced a 35% or greater reduction in spleen volume compared to 0.7% of patients receiving placebo ($P < 0.0001$). 45.9% of ruxolitinib treated patients regardless of their JAK2 mutational status experienced a $\geq 50\%$ improvement in constitutional symptoms as compared to 0.7% in the placebo group. Survival analysis on extended ruxolitinib therapy with a mean follow up of 52 weeks showed a statistically significant reduction in death with a hazard ratio of 0.499 (0.254, 0.98) and a probability of survival compared to placebo of 0.98 vs 0.90 and 0.84 vs 0.77 in patients with a baseline hemoglobin $>10\text{g/dL}$ and $<10\text{g/dL}$, respectively (27). In further subset analysis, patient age ≤ 65 years appeared to have a survival benefit over > 65 years of age with a HR 0.22 (0.06,0.84) with ruxolitinib therapy.

The drug therapy was uniformly ineffective in reversing histopathological abnormalities in the peripheral blood or marrow, eliminating marker cytogenetic abnormalities or reducing the

JAK2V617F allele burden to a degree associated with tyrosine kinase inhibitor therapy of BCR/ABL1 for chronic myeloid leukemia. The other limitation of the agent that has been the rapid return of splenomegaly following discontinuation of the drug and the occasional occurrence of life threatening syndromes attributed to the rapid elevation of cytokines. This “ruxolitinib withdrawal syndrome” has been described in 5 of the 47 MF patients treated at Mayo Clinic that had rapid discontinuation and the authors advise tapering the drug when possible in addition to upfront discussion with the patient regarding this potential drug associated serious adverse event (28).

The *COntrolled Myelofibrosis Study with ORal JAK2 inhibitor Treatment COMFORT-2* study was a randomized (2:1), Novartis sponsored, open-label phase III clinical trial conducted in nine European countries comparing ruxolitinib to best available therapy (BAT) (29). Hydroxyurea (46.6%), steroids (16.4%) and supportive therapy (32.9%) comprised the BAT arm. At a median age of 66 years, 219 patients with intermediate-2 or high risk MF were randomized (146 ruxolitinib, 73 BAT).

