10.4.2.2 Dose expansion

The cohort of 6 patients at the MTD and/or RPTD will be expanded by an additional 16 patients in order to further assess safety and tolerability. Thus the number of patients treated at the MTD and/or RPTD will be 22, which ensures that there is a 90% chance to detect any AE with a 10% incidence rate among patients treated at the MTD and/or RPTD. During this phase of the study, further defining of the biological activity of this combination will be explored. The primary endpoint of this portion of the trial is response rate by IWG-MRT criteria. We hypothesize a response rate of >40% in treated patients at C6D28 will constitute a positive primary endpoint. A positive response by IWG-MRT criteria includes SD, CI, PR, or CR. Since preclinical studies suggest a synergistic effect of the two agents in combination, we would expect a spleen response rate (>35% reduction in spleen volume by MRI or >50% reduction in palpable spleen) of >30% as was assumed in the COMFORT study. Since the proportion of patients obtaining this efficacy endpoint was 42%, we will have a target response for this secondary endpoint of >50%, and this will be reported in a descriptive manner.

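### The >50% spleen target rests on a 24-week, volume-only rate from COMFORT-1, but 10.6.2 counts responders at Week 12 and 10.4.2.2 counts an MRI-or-palpation composite

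*Combined protocol and SAP*

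**What the plan says.** **Section 10.6.2 (MRI/CT efficacy).** The endpoint is volume change from baseline to Week 12, or to end of study if that is earlier. Responders, with a reduction of at least 35%, are counted "at week 12 or end of study, whichever comes first), will be summarized in terms of percentage rates of response", with an exact binomial 95% interval. For the later scan the section promises only this: "Descriptive statistics for the volumetric reduction in spleen size and percent change (from baseline) at the end of week 24 will also be provided". It then sets the target: "this efficacy endpoint was 42% in COMFORT-1, we will have a target response for this secondary endpoint of >50" per cent.

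**Section 10.4.2.2 (dose expansion).** Spleen response is defined as ">35% reduction in spleen volume by MRI or >50% reduction in palpable spleen". The same reasoning follows: "Since the proportion of patients obtaining this efficacy endpoint was 42%, we will have a target response for this secondary endpoint of >50" per cent. The spleen sentences name no time point.

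**Source of the 42%, section 1.3.3.** On COMFORT-1: "The primary endpoint of this study was a reduction in spleen volume of at least 35% by either MRI/CT". The result: "At 24 weeks, 41.9% of patients treated with ruxolitinib experienced a 35% or greater reduction in spleen volume".

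**Assessments.** Section 7.2.2.3 schedules imaging at screening, C4D1 and C6D29/C7D1. Section 7.2.2.1 places the spleen assessment at the end of Cycle 6 (Day 169), by palpation compared with Cycle 1 Day 1 or by imaging volume.

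**Status.** Sections 10.4.2.2 and 10.6.2 both report the target descriptively. Section 10.8 excludes formal testing for secondary variables, and 7.2.2 calls efficacy beyond IWG-MRT response exploratory.

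**The concern.** The trial has one arm and no concurrent ruxolitinib-alone group, so the 42% is the plan's only stated anchor for calling a spleen response rate above 50% encouraging. That comparison is informative only if the trial counts what COMFORT-1 counted, at the time COMFORT-1 counted it. Followed as written, 10.6.2 yields a rate at a different time point and 10.4.2.2 yields a rate on a wider definition.

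The two sections also disagree with each other, because one target has two definitions. An analyst cannot tell which rate is to be set against 50%. A composite above 50% could come from patients who respond by palpation only, and could then be read as added benefit over ruxolitinib alone.

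**Working it through.** **1. Trace the 42%.** Section 1.3.3 gives 41.9% among 155 patients randomised to ruxolitinib. 0.419 × 155 = 64.9, and 65/155 = 41.9%, which rounds to 42%. The plan's figure is reproduced. It is a 24-week rate on MRI/CT volume only.

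**2. Place the scans on the calendar (28-day cycles, 28-day ruxolitinib induction).**

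| Scan | Study day | Weeks of combination | Weeks since first induction dose |
|---|---|---|---|
| C4D1 | 3 × 28 + 1 = 85 | 84/7 = 12 | (84 + 28)/7 = 16 |
| C6D29/C7D1 | 6 × 28 + 1 = 169 | 168/7 = 24 | (168 + 28)/7 = 28 |

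The rate in 10.6.2 uses the first row. The benchmark's 24 weeks corresponds to the second row on the combination clock. On the ruxolitinib clock the first row is 16 weeks, still short of 24.

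**3. Effect of the 'or'.** For volume response V and palpation response P at one time point, Pr(V or P) = Pr(V) + Pr(P and not V), which is at least Pr(V). The increment is the proportion responding by palpation only. The documents do not give it.

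**4. What above 50% means with 22 patients.** 11/22 is exactly 50%, so the target needs at least 12/22 = 54.5%. The Clopper-Pearson 95% interval for 12/22 is 32.2% to 75.6%, which includes 41.9%. The lower limit first passes 41.9% at 15/22, where it is 45.1%.

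**5. Chance of reaching the target.** With X binomial(22, p), Pr(X ≥ 12) is:

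| True rate p | Basis | Pr(X ≥ 12) |
|---|---|---|
| 41.9% | equal to COMFORT-1, volume only | 16% |
| 46.9% | palpation adds 5 points (assumed) | 31% |
| 51.9% | palpation adds 10 points (assumed) | 49% |
| 56.9% | palpation adds 15 points (assumed) | 67% |

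Only the first row uses a rate taken from the documents. The other three show how sensitive the target would be to an unknown increment.

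**6. Timing effect.** No Week 12 COMFORT rate is given, so neither its size nor its direction can be calculated. The COMFORT-2 figures (31.9% at 24 weeks, 28.5% at 48 weeks) do not cover Week 12.

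**The case against.** The strongest reply is that nothing depends on this target. It is descriptive, untested and unpowered, and the primary endpoint is IWG-MRT response. That stands, and it limits the severity. It does not make the comparison valid, because a descriptive rate set beside a named benchmark still has to measure the same thing.

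A second reply is that much of the remedy is already in the plan. Section 7.2.2.3 defines a 35% volume responder without limiting it to Week 12. Section 10.6.2 is already volume-only with an exact interval. Section 10.6.1 reports palpation separately at Weeks 12 and 24, although it is unclear whether that extends beyond the escalation phase. This also stands, and it is why the change is small. The Week 24 responder rate is still not planned, and the 'or' is still in 10.4.2.2.

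A reader might go further in four ways that the documents do not support:

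- **That 10.4.2.2 has the same timing fault.** Section 7.2.2.1 puts the spleen assessment at Day 169, and the response rate in 10.4.2.2 is timed at C6D28. The timing mismatch belongs to 10.6.2 only.
- **That Week 12 counting flatters, or penalises, the combination.** No direction can be derived.
- **That the 57% palpation rate on ruxolitinib alone in section 1.3.3 shows the composite target would be met without panobinostat.** That figure comes from another trial with doses up to 50 mg BID and no stated time point. Here ruxolitinib is 10 or 15 mg BID, and palpation is compared with Cycle 1 Day 1, after the induction month.
- **That the denominator is 16.** Section 10.6.2 says "The analysis will be restricted to patients in the expansion phase, who are dosed at the MTD and/or RPTD", but section 4.1 describes the expansion stage as 16 added to 6, and 10.8 carries the six forward as the first phase II patients. Both favour 22.

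**Conclusion.** Wrong as written, at low severity. Two separate mismatches stand on the text. In 10.6.2, a Week 12 responder rate is judged by a target derived from a 24-week rate. In 10.4.2.2, a volume-or-palpation composite is judged by a target derived from a volume-only rate, in conflict with 10.6.2.

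The composite can only equal or exceed the volume rate at the same time point; by how much is unknown. The 16% chance of reaching 12/22 assumes a true rate of 41.9% and 22 assessed patients. The rise to 31%, 49% or 67% depends entirely on the assumed increments. No primary result, sample size or decision rule is affected.

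**What to change.** In 10.4.2.2 and 10.6.2, tie the >50% target to one quantity: the MRI/CT volume responder rate (at least 35% reduction from screening) at C6D29/C7D1 in the 22 RPTD patients, with its exact 95% interval. Keep the Week 12 responder rate in 10.6.2 as an additional descriptive row. Remove the 'or' from 10.4.2.2 and report palpation response on its own line, from Cycle 1 Day 1 as in 7.2.2.1.

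The cost is a short amendment and one or two table rows. The scans and palpation are already scheduled in 7.2.2.3 and 7.2.2.1. The sponsor gives up the palpation route to the target, so the target may be slightly harder to meet than under the composite. The gain is a descriptive rate that matches its reference in time point and measure.
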